### **6.6.3 GEN3014 and Daratumumab Dose Modification Guidance and Stopping Criteria (Expansion Part B)**

#### **6.6.3.1 GEN3014 IV or Daratumumab SC Dose Modifications**

Any dose/dosage adjustment should be overseen by medically qualified study site personnel (principal or sub-investigator unless an immediate safety risk appears to be present).

Trial drug administration must be captured in the source documents and the electronic case report form (eCRF).

Dose modification of 16 mg/kg (ie, the RP2D) GEN3014 IV or 1800 mg daratumumab SC (increase or decrease) is not permitted. Dose delay is the primary method for managing GEN3014 or daratumumab-related toxicities.

##### **6.6.3.1.1 GEN3014 IV or Daratumumab SC Dose Delays**

If any of the following criteria are met and the toxicity is more than expected for the underlying MM, GEN3014 infusion or daratumumab injection must be held to allow for recovery from toxicity as noted below. If attribution is unclear, then GEN3014 or daratumumab should be held until recovery from toxicity as noted below:

The criteria for a delay are:

- Grade 4 hematologic toxicity, except for grade 4 lymphopenia
- Grade 3 thrombocytopenia with bleeding
- Febrile neutropenia
- Neutropenia with infection, of any grade
- Grade 3 or higher non-hematologic toxicities with the following exceptions:
  - Grade 3 nausea that responds to antiemetic treatment within 7 days
  - Grade 3 vomiting that responds to antiemetic treatment within 7 days
  - Grade 3 diarrhea that responds to antidiarrheal treatment within 7 days

- Grade 3 fatigue that was present at baseline or lasts for <7 days after the last administration of trial drug
- Grade 3 asthenia that was present at baseline or lasts for <7 days after the last administration of trial drug

Administration of trial drug may be restarted upon recovery from toxicity to Grade 2 or baseline, with the exception that Grade 2 laryngeal edema or Grade 2 bronchospasm must be fully recovered.

If a dose delay occurs, then PK and pharmacodynamic assessments should be performed on or relative to the actual day of trial drug administration, not on the original scheduled administration day.

#### 6.6.3.1.2 GEN3014 IV or Daratumumab SC Skipped Doses

Other than on Day 1 of a cycle, if any “within-cycle” daratumumab administration does not commence within the prespecified window (Table 6-4) of the scheduled administration date, then the dose will be considered a skipped dose. Administration may resume at the next planned dosing date. A minimum of 4 days between trial drug doses must be observed. A skipped dose will not be made up.

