#### 4.1.4 Expansion Part B (Randomized H2H)

If the preliminary efficacy and safety are judged to be favorable in the initial 10 anti-CD38 mAb-naïve subjects with RRMM who received 16 mg/kg or 24 mg/kg (in the Dose Escalation or Expansion Part A), approximately 80 anti-CD38 mAb-naïve subjects with RRMM will be randomized in a 1:1 ratio to receive:

- GEN3014 IV at the RP2D (N=40), or
- Daratumumab SC at the approved dose of 1800 mg (N=40)

The aim of the head-to-head comparison between GEN3014 IV and daratumumab SC is to evaluate the efficacy and maximum Cycle 3 Day 1 Ctrough level of study treatments in at least 40 subjects on each treatment arm. To ensure the collection of sufficient efficacy, PK, and safety data, after approximately 80 subjects are randomized, additional enrollment to either treatment arm can be implemented to replace:

- Subjects who are randomized but never receive the study treatment; and/or
- Subjects who discontinue the study treatment prematurely prior to the Cycle 3 Day 1 dosing

A maximum of 90 subjects will be treated.

The administration schedule will be the same as in the Dose Escalation (see Section 6.1), except that the first dose of daratumumab SC will not be split between Days 1 and 2.

Randomization will be stratified by body weight at baseline ( $\leq 70$  kg vs  $> 70$  kg), CCI [REDACTED]. See Sections 5.1.3 and 5.2.2 for inclusion and exclusion criteria.

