### 9.1 Statistical Hypotheses

Objectives and endpoints of the trial are stated in Section 3. There are no pre-defined hypotheses for this trial. The escalation part is designed to determine the RP2D and MTD (if reached), and the Expansion Part A to assess the anti-tumor activity of GEN3014.

In the Expansion Part B (Randomized H2H), the response ratio and the geometric mean ratio of  $C_{\text{trough}}$  on Cycle 3 Day 1 will be derived to describe the proportion of effect of daratumumab SC retained by GEN3014 IV as compared to daratumumab SC. The comparison serves as a preliminary estimation of the relative effect of the 2 anti-CD38 mAb molecules.

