## **9.3 Populations for Analyses**

**Full Analysis Set (FAS):** The FAS and safety set are defined in the same way and will comprise all enrolled subjects who receive at least 1 dose of trial drug (GEN3014 or daratumumab SC). In case of any deviations from planned dosing, subjects will be treated as per actual dosing.

The FAS will be used to summarize efficacy and safety analyses.

**Response Evaluable Set (RES):** Comprises all subjects in the FAS that at the timing of data cutoff date (for any interim reporting of the ongoing data):

- have measurable disease at baseline;
- had  $\geq 1$  on-treatment disease assessment;
- have died within 60 days of first trial treatment without post-baseline disease assessment (these are included as non-responders)

**Safety Set:** See definition for FAS.

**Per-Protocol Set:** Not applicable

**Dose-Determining Analysis Set (DDS):** The DDS will include all FAS subjects in the Dose Escalation part who meet the minimum exposure criterion and have sufficient safety evaluations or experience a DLT during the first 28 days of dosing (ie, in Cycle 1).

A subject will meet the minimum exposure criterion if the subject receives 4 out of the 4 preplanned doses during the DLT period. (The 2 initial split doses in Day 1 and Day 2 account for 1 preplanned dose.)

**Pharmacokinetic Analysis Set 1 (PAS1):** The PAS1 will include all enrolled subjects who receive at least 1 dose of trial drug (GEN3014 or daratumumab SC) and who provide at least 1 evaluable PK sample.

**Pharmacokinetic Analysis Set 2 (PAS2):** The PAS2 will include all enrolled subjects who received all 8 weekly GEN3014 or daratumumab SC doses in Cycles 1 and 2 with the cumulative dose administered amounting to 80% to 125% of the planned dose and provided a predose PK blood sample on Cycle 3 Day 1.

**Immunogenicity Analysis Set (IAS):** The IAS will include all enrolled subjects who receive at least 1 dose of trial drug (GEN3014 or daratumumab SC) and have a baseline and at least 1 evaluable on-treatment ADA sample.

**Biomarker Analysis Set (BAS):** The BAS will include all enrolled subjects who receive at least 1 dose of trial drug (GEN3014 or daratumumab SC) and have at least 1 evaluable biomarker sample.

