#### **9.4.6.1 Cycle 3 Day 1 Trough Concentration**

The PAS2 will be used for the analyses presented in this section.

The  $C_{trough}$  on Cycle 3 Day 1 is defined as a secondary endpoint in Expansion Part B, as part of the comparison of the 2 anti-CD38 mAb molecules. The  $C_{trough}$  levels in the 2 arms will be compared by calculating the geometric mean ratio and the corresponding 90% CI.

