### **4.7 Pharmacokinetic Analysis Set 2 (PAS2)**

The PAS2 will include all enrolled subjects who received all 8 weekly GEN3014 or daratumumab SC doses in Cycles 1 and 2 with the cumulative dose administered amounting to 80% to 125% of the planned dose and provided a predose PK blood sample on Cycle 3 Day 1.

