### 5.1.2 Visit Windows

Any efficacy analysis that utilizes time to event approach will be based on an exact determination of time from C1D1 to the date of event/censoring.

Unless otherwise stated data will be presented as collected on the nominal visits, that is, if data are collected as part of CxDy visit in the CRF it will be presented as such in analyses irrespective of the subject's adherence to the protocol visit schedule and actual collection date. Unscheduled visits will not be displayed summaries but will be listed.

Disease assessments are not tied to nominal visits in eCRF but are scheduled to be performed on a regular basis per protocol. The analysis time window listed in Table 4 and Table 5 will be used to slot actual disease assessment date into planned disease assessment schedules for summary statistics for RRMM, AML and R/R DLBCL, respectively. The visit window is mainly for display disease assessment in a chronological order and will generally not be used in actual analysis.

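### PAS2 sets no limit on days since the eighth weekly dose, so the Part B Cycle 3 Day 1 trough ratio can mix planned 7-day troughs with later ones

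*Protocol*

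**What the plan says.** Protocol 4.1.4 says that the aim of the head-to-head "is to evaluate the efficacy and maximum Cycle 3 Day 1" trough level of the two treatments. Section 9.1 says that the response ratio and the geometric mean ratio of that trough "will be derived to describe the proportion of effect of daratumumab SC retained by GEN3014 IV". Under 9.4.6.1 the trough levels in the two arms "will be compared by calculating the geometric mean ratio and the corresponding 90% CI", using PAS2.

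Five rules decide which concentrations enter the ratio:

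- **Delay (6.6.3.1.1).** A dose is held until recovery from toxicity. After a delay, "PK and pharmacodynamic assessments should be performed on or relative to the actual day of trial drug administration".
- **Skip (6.6.3.1.2 and Table 6-4).** The rule that turns a late dose into a skipped dose begins "Other than on Day 1 of a cycle". For Cycles 3 to 6, Table 6-4 sends a dose held more than 7 days to the next two-weekly date.
- **Outer check (6.6.3.1.3).** After more than 28 days of interruption for toxicity, the sponsor must be consulted about continuing.
- **PAS2 (protocol 9.3, SAP 4.7).** The subject must have had all eight weekly doses, "with the cumulative dose administered amounting to 80% to 125% of the planned dose", and must have "provided a predose PK blood sample on Cycle 3 Day 1". There is no condition on time since the last dose.
- **Visit handling (SAP 5.1.2).** Unless stated otherwise, data are shown at the nominal visit irrespective of the subject's "adherence to the protocol visit schedule and actual collection date".

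Neither document describes a time adjustment or a sensitivity analysis for the trough ratio.

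**The concern.** A trough depends directly on how long ago the last dose was given. PAS2 controls the amount of drug received but leaves this second determinant open. A subject whose Cycle 3 Day 1 dose is held for toxicity keeps the Cycle 3 Day 1 label, stays in PAS2, and contributes a concentration that is low partly because of extra washout.

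The set is also uneven. A hold of more than 3 days on Day 8, 15 or 22 of Cycles 1 and 2 makes a skipped dose and removes the subject from PAS2. A hold at Cycle 3 Day 1 need not.

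Holds follow toxicity, and the arms receive different drugs by different routes, so holds need not balance. If they do not, the ratio leans against the arm with more of them, and the plan as written would present that as a difference in PK between the molecules.

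**Working it through.** The documents give no precision or power figure for the trough ratio, so there is none to reproduce.

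**Inputs from the documents.** Cycle 2 doses fall on Days 1, 8, 15 and 22 of a 28-day cycle (6.1.6.1). The visit window is ±3 days (Table 1-12). At least 4 days must separate doses (6.6.3.1.2). About 40 evaluable subjects per arm are planned (9.2.3).

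**Assumptions, none of them in the documents.** Elimination half-life h of 10 to 25 days with first-order decline; between-subject CV of 40% to 60%; the difference Δ between arms in the share of PAS2 subjects held.

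**Step 1, planned interval.** Cycle 2 Day 22 is study day 28 + 22 = 50 and Cycle 3 Day 1 is day 57, so 57 − 50 = 7 days. With each visit inside its window, the latest sample comes at (57 + 3) − (50 − 3) = 13 days. The earliest would be (57 − 3) − (50 + 3) = 1 day, which the minimum dose gap raises to 4. The protocol's own windows therefore allow 4 to 13 days.

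**Step 2, how late a kept sample can be.** There are two readings:

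- *Table 6-4 covers Day 1.* A hold of up to 7 days is kept, giving 7 + 7 = 14 days after an on-schedule eighth dose. A longer hold restarts at the next two-weekly date, presumably leaving no Cycle 3 Day 1 predose sample.
- *The Day 1 exemption governs.* Holds of 14, 21 or 28 days give 21, 28 or 35 days. Sponsor consultation starts only after more than 28 days of toxicity interruption.

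**Step 3, effect on one trough.** The fraction of the 7-day value left after d extra days is 2^(−d/h).

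| Days late | h = 10 | h = 15 | h = 25 |
|---|---|---|---|
| 7 | 0.62 | 0.72 | 0.82 |
| 14 | 0.38 | 0.52 | 0.68 |

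For SC dosing with an assumed absorption half-life of 1 to 4 days, the 14-day row becomes 0.38–0.49, 0.53–0.62 and 0.68–0.76, so the picture is similar.

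**Step 4, effect on the ratio.** If the share held differs by Δ, the geometric mean ratio is multiplied by 2^(−Δd/h).

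| Δ | 7-day holds | 14-day holds |
|---|---|---|
| 5 points | 0.98–0.99 | 0.95–0.98 |
| 10 points | 0.95–0.98 | 0.91–0.96 |
| 20 points | 0.91–0.96 | 0.82–0.93 |

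**Step 5, against the interval's width.** The 90% CI is the estimate times or divided by exp[t(0.95; 78) × √ln(1 + CV²) × √(2/40)], which is 1.15, 1.19 and 1.23 at CV 40%, 50% and 60%. At CV 50% I simulated lognormal troughs with a share Δ of one arm late and none of the other. Coverage of the nominal 90% CI for the ratio of 7-day troughs, over h = 10 to 25, is:

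| Δ | 7-day holds | 14-day holds |
|---|---|---|
| 10 points | 87%–89% | 79%–88% |
| 20 points | about 77%–88% | 53%–82% |

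**The case against.** The strongest reply concerns Table 6-4. From Cycle 7 dosing is on Day 1 only, so its Cycle 7+ row can apply only if the table reaches Day 1 doses. The exemption sentence also names only daratumumab, although its heading and the table cover both drugs. On that reading no kept hold exceeds 7 days, and the 14-day columns fall away. This stands. A reader might infer from 6.6.3.1.2 that the interval has no limit at all. The documents do not settle that, and even if the exemption governs, 6.6.3.1.3 brings in the sponsor after 28 days.

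Second, PAS2 subjects have had all eight weekly doses, and the protocol places infusion reactions mainly at the first infusion or in Cycle 1. A 10-point difference means 4 more of 40 subjects in one arm with a qualifying toxicity around Week 9. No hold rates are given, and equal holds largely cancel. This stands too: the between-arm differences above are illustrations, not forecasts.

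Third, the trough is defined as the predose concentration, and a held subject's really is lower. That is a legitimate estimand. It fits less well with 9.1, which uses the ratio to describe the effect retained by one molecule relative to the other, and PAS2 already screens for dose received.

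Fourth, the endpoint is secondary, with no hypothesis, margin or decision rule. Individual concentration curves are planned (protocol 9.4.6), and the SAP plots GEN3014 by actual time (5.6.1.1). Late samples could therefore be seen, but the reported ratio would still include them.

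**Conclusion.** The gap is real under either reading of the delay rules: the sample moves with the dose, PAS2 keeps it, and nothing limits or adjusts for days since the last dose. Its size is modest on the narrower reading of Table 6-4, where a 10-point difference in holds moves the ratio by 2% to 5%. It is larger, 4% to 9%, if 14-day holds are kept. At a 5-point difference it is small either way. These figures rest on the assumed half-lives, first-order decline and hold differences.

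A reader might also infer that the comparison is biased against GEN3014. The documents give no ground for a direction, since they do not say which arm will have more holds at Cycle 3 Day 1. ORR is not touched. This is a point to consider, of medium confidence, about a descriptive secondary endpoint.

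**What to change.** Before database lock, add one condition to PAS2 in protocol 9.3 and SAP 4.7: the Cycle 3 Day 1 predose sample must fall 4 to 13 days after the eighth weekly dose. This is the range from Step 1, so no subject is dropped whose visits all kept to protocol windows. Report the ratio in PAS2 as now defined as a sensitivity analysis. If the sponsor prefers not to add a toxicity-related exclusion to the main PK set, the reverse works equally well: keep PAS2 and make the windowed ratio the sensitivity analysis.

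The change works under either reading of Table 6-4. Administration dates and times are already recorded (protocol 6.5), so no extra blood draw is needed.

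The cost is one clause, one table and a few subjects. If 5% to 20% of each arm were late (assumed), 2 to 8 of 40 would leave the windowed set, and the 90% CI factor at CV 50% would widen from 1.19 to between 1.20 (38 per arm) and 1.22 (32 per arm).

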**Table 6-4 GEN3014 IV or Daratumumab SC Administration Schedule for Dose Delays**

Cycles	Frequency	Dose Held	Dosing Restart
1 and 2	Weekly (q1wk)	>3 days	Next planned weekly dosing date
3 to 6	Every 2 weeks (q2wks)	>7 days	Next planned every 2 weeks dosing date
7+	Every 4 weeks (q4wks)	>14 days	Next planned every 4 weeks dosing date

#### 6.6.3.1.3 Treatment Continuation Following GEN3014 IV or Daratumumab SC Delay

If the treatment is interrupted for >28 days due to toxicity, but the event has resolved to grade 2 or baseline, consult with the sponsor to discuss continuation on study. If not approved, subject should be discontinued from study treatment and proceed to End of Treatment visit. Subjects missing  $\geq 3$  consecutive planned doses of trial drug for reasons other than toxicity should be withdrawn from treatment, unless, upon consultation with the sponsor and the review of safety and efficacy, continuation is agreed upon. Systemic administration-related reactions may occur upon re-initiation of daratumumab after a prolonged delay in treatment.

## 6.7 Prior and Concomitant Therapies

### 6.7.1 Prior Anti-Cancer Therapies

Prior anti-cancer therapies received from the time of initial diagnosis and until 14 days before administration of the first dose of GEN3014 should be reported. These include chemotherapy, radiation therapy, surgery, antibody, CAR-T cell therapy, transplantation, investigational drug, etc.

The best response, reason for discontinuation, dates of treatment, and date of progression should be reported for prior anti-cancer therapies.

## **6.7.2 Other Prior Therapies**

Any other medication or vaccine (including over-the-counter or prescription medicines, vitamins, and/or herbal supplements) received within 21 days before administration of the first dose of GEN3014 must be documented.

## **6.7.3 Concomitant Therapies**

The subject must be told to notify the trial site about any new medications (including over-the-counter or prescription medicines, vitamins, and vaccines) he/she takes after the start of GEN3014 or daratumumab SC treatment. All medications (other than GEN3014 or daratumumab SC) and therapies (eg, physical therapy, herbal/natural medications, and blood transfusions) administered during the trial (ie, beginning with administration of the first dose of GEN3014 or daratumumab SC until 30 days after the last dose of GEN3014 or daratumumab SC) must be documented.

Investigators may prescribe concomitant medications or treatments deemed necessary to provide adequate supportive care except for those medications identified as “prohibited” (Section 6.7.3.3).

Concomitant therapies should also be documented beyond 30 days only in conjunction with SAEs that meet the criteria in Section 10.3.

### **6.7.3.1 Recommended Therapies**

The following therapies are recommended as prophylaxis during the trial.

#### **Drugs affecting bone structure and mineralization**

All patients receiving primary myeloma therapy should be given bisphosphonates or denosumab per National Comprehensive Cancer Network (NCCN) guidelines 2022 (NCCN, 2022). Commercially available bisphosphonates or denosumab, should be used according to the manufacturer’s recommendations, as described in the prescribing information and per institutional guidelines (Anderson et al., 2018). The initiation and changing of the bisphosphonate or denosumab therapy during the trial should be discussed with the sponsor to avoid interference with the evaluation of the bone disease progression.

#### **Therapy for Tumor Lysis Syndrome**

It is recommended that high-risk subjects (ie, those with a high tumor burden) should be treated prophylactically in accordance with local standards (eg, rehydration, diuretics, allopurinol 300 mg daily, and medication to increase urate excretion).

All subjects should be monitored for symptoms of TLS (see Section 10.3.7). Management of TLS, including dehydration and abnormal laboratory test results such as hyperkalemia, hyperuricemia, and hypocalcemia, is highly recommended.

#### **Prophylaxis for IRRs or sARRs**

All subjects will receive prophylactic therapy to prevent IRRs or sARRs during the Treatment period, as described in Section 6.2.

#### **Therapy for *Pneumocystis carinii***

*Pneumocystis carinii* pneumonia prophylaxis should be considered, as per institutional guidelines.

#### **Prophylaxis for Herpes Zoster Reactivation**

Prophylaxis for herpes zoster reactivation should be initiated within 1 week after starting GEN3014 or daratumumab SC and continue for 3 months following treatment. Acceptable

antiviral therapy includes acyclovir (eg 400 mg given orally 3 times a day, or 800 mg given orally 2 times a day or per institutional standards), famcyclovir (eg, 125 mg given orally, twice a day or per institutional standards), or valacyclovir (eg, 500 mg given orally, twice a day or per institutional standards).

#### **Prevention of steroid induced gastritis**

Dexamethasone and other steroids may induce gastritis. Medications to prevent gastritis are permitted per institutional guidelines, for example proton pump inhibitors (omeprazole or equivalent) or sucralfate, or H2 blockers (ranitidine or equivalent).

#### **Infection Prophylaxis**

Prophylactic use of antibiotics is highly recommended due to the susceptibility of patients with MM to infections. Prophylactic administration of antibiotics should be considered and dependent on institutional guidelines.

#### **6.7.3.2 Permitted Concomitant Medications and Therapies**

In addition to recommended therapies (see Section 6.7.3.1), the following concomitant medication and therapies are permitted during the trial:

- SARS-CoV-2 vaccine is generally permitted, including mRNA-based, protein-based, or non-replicating viral vector-based vaccines. Consider choosing an appropriate type of SARS-CoV-2 vaccine and consult with an infectious disease expert if desired. Note: SARS-CoV-2 vaccine should not be administered during the DLT period.
- G-CSF and other hematopoietic growth factors may be used in the management of acute toxicity, such as febrile neutropenia and  $\geq$  grade 3 neutropenia, when clinically indicated or at the investigator's discretion. In case of  $\geq$  grade 3 neutropenia, use of growth factors is mandated.
- Erythropoietin
- Red blood cell and platelet transfusions, if clinically indicated
- Multivitamins, vitamin D, calcium and supplements, for prevention of weight loss
- Prescribed medicinal cannabinoids as palliative therapy
- Stool softeners if needed, high fiber diet and adequate hydration to prevent constipation
- Adequate hydration is recommended for prevention of myeloma-related kidney disease
- Local palliative radiotherapy for bone fracture/pain associated with MM and that is refractory to narcotic analgesics (because pathologic bone fractures do not by themselves fulfill a criterion for disease progression)
- Typically, IV contrast is not used in CT scanning of subjects with secretory MM due to risk to the kidney. If administration of IV contrast is necessary, adequate precautions including hydration are recommended.

The trial site will supply supportive medication, eg, pre-infusion medication, post-infusion medication, anti-viral medication.

